#### \* 5.14i What data sets will you be matching?

For those who signed a medical release form, medical records data will merged with data collected by Mildmay staff when offering PrEP to people who test HIV-negative, such as: gender, age, occupation, marital status, and residency status (permanent/transient or mobile, and if so, number of times away from the community in the past 3 months).

\* 5.14j What information will be used to perform matching (e.g. name, Social Security numbers, GPS, etc.)?

Mildmay client ID

View: Detail Create/Edit

#### 5.10 Social-Behavioral and Other Interventions

You previously indicated that your research involves a social behavioral or other intervention. Please provide the following details about the intervention.

#### \* 5.10a Provide a brief description of the intervention and how it will be carried out.

The pilot interventions will occur on Nakiwogo and Kigungu landing sites, Wakiso District, Lake Victoria, Uganda. We will offer PrEP to eligible HIV-negative fisherfolk who are tested at Nakiwogo and Kigungu. PrEP will be provided by Mildmay Uganda through the national PrEP program, administered by the Ugandan Ministry of Health.

Mildmay conducts regular (e.g., weekly) community mobilization and healthcare outreach events at the two landing sites, in which HIV testing and PrEP are offered, ART is given to those who test HIV-positive, and other healthcare services are provided. Specifically, to de-stigmatize HIV testing so that healthcare workers are not associated solely with HIV, staff have basic medical supplies on hand in addition to what is needed for HIV testing (e.g., de-worming pills). During community mobilization, Mildmay staff, Village Health Team members (VHTs), and Beach Management Unit (BMU) leaders will conduct outreach with fisherfolk prior to events (e.g., home visits, radio advertisements) and mobilize fisherfolk during events (e.g., using bullhorns), using key messages developed from the Aim 1 formative research to raise awareness around PrEP. During the testing event, BMU leaders will deliver PrEP messages (e.g., via bullhorns), and HIV testing counselors will convey PrEP information in one-on-one conversations. Specifically, Mildmay HIV counseling and testing staff will introduce PrEP to adult fisherfolk (≥18 years-old) who test HIV-negative at post-test counseling using messages developed in Aim 1.

At Nakiwogo, events will be held in a public temporary space (e.g., tent, church) in partnership with Entebbe Hospital, and at Kigungu, Mildmay staff will use space in the nearby public Kigungu Health Center III to test and treat clients during community mobilization events. In Nakiwogo only, we will conduct an enhanced behavioral PrEP intervention to compare to the standard of care in Kigungu. Specifically, in Nakiwogo, we will have a three-pronged intervention: 1) During healthcare outreach events in Nakiwogo, we will conduct PrEP workshops, in which people who want to know more about PrEP can learn basic facts about PrEP and also can be taught skills about how to advocate for PrEP in their community. These PrEP workshops will be conducted by master trainers, who are Mildmay staff who have been trained by the Ugandan Ministry of Health to conduct health workshops and trainings. 2) Check-in Calls: To support PrEP adherence, healthcare workers will call PrEP users regularly (e.g., every 1-2 weeks), to check in about any questions and to remind them of the next date and place to pick up refills. Calls will be more frequent after PrEP initiation, to ask about side effects. 3) To support PrEP adherence, healthcare workers will encourage PrEP users to select an adherence supporter, who is a family member or friend to whom they disclose their PrEP use. The adherence supporter agrees to remind them to adhere to PrEP and get refills. Healthcare workers will ask the PrEP user for the name and contact information, as well as the age and gender, for the adherence supporter, so that the adherence supporter can be contacted to remind them about refills, as well as if the PrEP user does not show up for a refill. All Adherence Supporters will also be invited to the intervention workshop, which is open to all community members. Note that the first intervention component (PrEP workshop) will be adapted from our current work in Uganda on prevention advocacy among people living with HIV (2016-0227; 2021-N0155). The last two intervention components are standard practices for people living with HIV on antiretroviral treatment, and will be adapted for PrEP users; provider guidance for adherence supporters will also be adapted from our current work in Botswana (2019-0253). To train master trainers and healthcare

providers for the intervention, we have modified Ugandan Ministry of Health PrEP training slides for healthcare providers and counselors, tailoring them based on the Phase 1 formative work and adding issues of importance to fisherfolk communities. We have received permission from the Ugandan Ministry of Health to make these modifications, and we are regularly meeting with the Ugandan Ministry of Health to update them about the study, and to help develop the intervention.

Per their usual Ministry of Health compliant procedures for PrEP, Mildmay healthcare providers will use an assumed consent procedure for providing PrEP. That is, individuals who attend an HIV testing event at which PrEP is being provided are assumed to consent to being prescribed PrEP when appropriate per Uganda Ministry of Health guidelines. Mildmay providers will draw blood to screen for PrEP contraindications [HIV-1 infected or evidence of possible acute HIV infection; allergy to Tenofovir Disoproxil Fumarate (TDF) and/or Emtricitabine (FTC); poor renal function; unwilling/unable to return for 3-monthly HIV testing, counseling and safety monitoring visits; weight <35kg]. Those eligible can obtain PrEP during Mildmay's outreach events, either in a temporary community-based venue at Nakiwogo, at Entebbe Hospital near Nakiwogo, or at Kigungu Health Centre III. Per Ministry of Health guidelines, most fisherfolk are eligible for PrEP as members of a high risk key population (with a high prevalence of multiple partners, transactional sex, alcohol use/abuse, serodiscordant relationships, and inconsistent condom use).

Update: After completion of the intervention in the intervention site, Nakiwogo (in Sept 2022), the implementing partner will provide the intervention to the comparison site, Kigungu. We will continue to collect de-identified PrEP user data to evaluate implementation at the comparison site.

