#### STUDY BASICS

#### 1. \* 3.1 Title of study

Evaluation of the Implementation of PrEP Provision for Ugandan Fisherfolk

2. \* 3.2 Brief summary or abstract. Note: this was populated from question 1.1c on the prescreener. Using this information please provide a brief summary or abstract of the study. Describe its purposes, study methods (i.e., participants, procedures, data sources), and expected results.

Please note that this is a transfer from RHINO 1.0, ID 2019-0571

Worldwide, fisherfolk are at an exponentially higher risk for HIV than the general population in their regions. In Ugandan fisherfolk communities, HIV prevalence is estimated to be 15-40% - much higher than in the general Ugandan population, for which HIV prevalence is estimated to be 5.9% among those aged 15-49. It is estimated that fisherfolk represent 5% of the population, and about 10% of the labor force is involved in the fisheries sector; fishing regions (lakes, rivers, etc.) cover about 20% of Uganda. Fisherfolk include fishermen and their families, people who support the fish trade business (e.g., fish vendors, boat off loaders), and commercial sex workers (CSWs) who live in fishing communities. A previous RAND study (led by [name]) with Makerere University School of Public Health, and Mildmay Uganda tested home-based and event-based antiretroviral therapy (ART) distribution models. This study will build on the previous findings and apply them to the development and testing of two PrEP delivery models for high-risk HIV-negative fisherfolk following HIV testing.

We propose to explore the acceptability and feasibility of PrEP, and to develop and compare the implementation of two interventions to promote PrEP use among fisherfolk: community-based vs. healthcare facility-based PrEP provision. We will partner with the Ministry of Health throughout the project, regularly meeting with its PrEP Technical Working Group to discuss study results and determine next steps for policy and national implementation.

The Specific Aims are:

- 1. To conduct formative qualitative research to examine barriers to and facilitators of PrEP uptake, and to obtain input on acceptable PrEP messaging and provision, for fisherfolk communities on Lake Victoria, Uganda.

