- 2. To conduct a mixed-methods analysis comparing the implementation of community-based vs. healthcare facility-based PrEP provision for fisherfolk communities on Lake Victoria, Uganda. When this study was initially proposed, the intent was to purchase and supply PrEP to study participants as it was not widely used in the country as a whole, or in fishing communities. Since the study was funded, PrEP use has become more widespread in Uganda and is provided by Mildmay Uganda via a Ugandan Ministry of Health program. As a result, the study will no longer purchase and provide PrEP through the grant, and instead will evaluate enhancements (i.e., behavioral interventions) to the standard of care for providing PrEP in Ugandan fishing communities.

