#### **Future Contact After Research Ends**

- 18. \* 6.10e After the project ends, is there a possibility that the participants will be contacted to participate in any future research (including research conducted on other topics by other research teams) because of their participation in this study? No
- 19. Recruitment Procedures
- 20. \* 6.11 Will you be recruiting participants for this population on this study? Yes No
  - \* 6.11a Please describe the step-by-step recruitment procedures for this study population. Provide details: who, what, where, when, and how.

All recruitment activities will be conducted by Makerere University School of Public Health personnel who are part of this study team.

Aim 1: We will recruit approximately 10-15 stakeholders (including Mildmay healthcare providers who work with fisherfolk, Beach Management Unit (BMU) leaders, Village Health Team (VHT) members, and policymakers at the Ugandan Ministry of Health). Stakeholders will be identified by Mildmay and Makerere University School of Public Health Investigators (e.g., based on their professional and workplace connections, such as at Mildmay, at the Ministry of

Health, and in fisherfolk communities) and referred to the study interviewer. Stakeholders will be interviewed at their workplace or a private space convenient for them.

Aim 2: To further assess acceptability of the PrEP interventions, we will conduct semi-structured interviews with 10 healthcare providers (e.g., counselor, lab technician, nurse, doctor, master trainers who conduct intervention sessions; 5 each for Kigungu and Nakiwogo) who deliver PrEP and 10 community stakeholders (e.g., BMU members, VHTs; 5 each for Kigungu and Nakiwogo; sample can overlap if they deliver care in both communities). They will be recruited during a testing/PrEP delivery event or through Ugandan study team contacts (e.g., the team is works with other healthcare providers and community leaders at the outreach events). Interviews will be conducted after 6 months of implementation of the PrEP intervention.

\* 6.11b Do you have recruitment materials (e.g. advertisements, flyers, letters of introduction, email invitations, and reminders) in draft or final form ready to upload? No

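### Study-developed Aim 1 messaging is planned at both landing sites, so Kigungu is not plain standard of care, and a before/during change cannot be credited to the three-part package alone

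*Combined protocol and SAP*

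**What the plan says.** **Origin of the messages.** Section 3.2 makes it part of Aim 1 "to obtain input on acceptable PrEP messaging and provision". The messages are therefore a product of this study. Under Aim 2 the study "instead will evaluate enhancements (i.e., behavioral interventions) to the standard of care for providing PrEP in Ugandan fishing communities".

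**Where they are used.** Section 5.10a, which answers the form's request to describe the intervention, begins "The pilot interventions will occur on Nakiwogo and Kigungu landing sites". It continues: "Mildmay conducts regular (e.g., weekly) community mobilization and healthcare outreach events at the two landing sites". Within that account, mobilisers work "using key messages developed from the Aim 1 formative research to raise awareness around PrEP", and counsellors introduce PrEP to adults "who test HIV-negative at post-test counseling using messages developed in Aim 1". Neither statement is restricted to one site.

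**The comparator.** The same section then says: "In Nakiwogo only, we will conduct an enhanced behavioral PrEP intervention to compare to the standard of care in Kigungu". It lists three components at Nakiwogo: workshops, check-in calls and adherence supporters. Messaging is not among them. The section adds that provider training slides were tailored from the formative work, without saying whether Kigungu's providers are trained with them.

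**The analysis.** The SAP models persistence (PrEP possession at 6 months, and a possession ratio above 80%) by logistic regression on a before/during indicator with age and gender. It names neither site, has no site or site-by-time term, and does not mention the messages.

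**The concern.** Two things follow if the text is applied as written.

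First, the comparator label does not match the care described. Kigungu would receive usual PrEP provision plus behavioural content that the study developed. The Aim 2 objective is framed against the standard of care, so that condition has to be defined correctly.

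Second, messaging is neither a listed component of the intervention nor a stated part of usual care. If it started when the intervention started, it is one more thing that changed between the two periods. A single time coefficient would absorb it, and the result could be reported as the effect of workshops, calls and supporters.

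**Working it through.** The documents give no effect size, power calculation or persistence rate, so there is no plan figure to reproduce. The check sets the passages side by side and then decomposes the contrasts.

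**Step 1. Is messaging planned at Kigungu?** Section 5.10a opens with both sites, locates the outreach at both, and describes the Aim 1 messages inside that outreach. The words limiting delivery to Nakiwogo appear only afterwards and attach to the three-component package. On the text, the answer is yes.

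**Step 2. Is messaging new during the intervention?** Section 5.10a uses the future tense. Section 6.11a (HIV-negative fisherfolk, Aim 2) describes current outreach in the present tense and does not mention Aim 1 messages. Together these suggest a new element. No passage dates it.

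The intervention itself is hard to place. Section 5.10a has it completed at Nakiwogo in September 2022; a 6-month intervention would then start near March 2022. Section 5.14b gives a window of March 2021 to September 2022, about 18 months. Read as 6 months before, 6 during and 6 after, it puts the intervention at about September 2021 to March 2022. The two readings differ by about 6 months. Aim 1 interviews were expected from 6/15/2020 (Part 4C), so messages could have been in use before either start.

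**Step 3. What each contrast contains.** Let P be the effect of the three components on persistence, M the effect of messaging that starts between the periods (zero if it was already in use throughout the pre-period), and T secular change, with subscripts N and K for the sites.

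- Nakiwogo before/during = P + M_N + T_N
- Kigungu before/during = M_K + T_K
- Difference in changes = P + (M_N − M_K) + (T_N − T_K)

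The first line does not identify P. The third equals P only if messaging effects and trends are the same at both sites, and P is then the gain over messaging-enhanced care. The SAP contains only a before/during contrast, which corresponds to the first line if it is fitted to Nakiwogo.

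**Step 4. Illustration, by assumption only.** Take P = 10 percentage points, no secular change, equal messaging effects at both sites, and M from 0 to 10 points.

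| M | Nakiwogo change = P + M | Excess over P = M/P | Difference in changes = P | Shortfall against total gain = M/(P + M) |
|---|---|---|---|---|
| 0 | 10 | 0% | 10 | 0% |
| 5 | 15 | 50% | 10 | 33% |
| 10 | 20 | 100% | 10 | 50% |

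The table shows the direction of each distortion and that both vanish at M = 0. It is not evidence about the size of M.

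**The case against.** The strongest reply is that messaging used at both sites is simply background care. A comparison over care as delivered at both sites is a legitimate pragmatic question, and shared messaging does not bias it for the three components. This stands. What shared messaging changes is the meaning of the contrast, and it understates the gain over usual care only if messaging itself works.

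Three further points also stand:

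- **Outcome.** The messages aim at awareness and at introducing PrEP, while the SAP outcomes are persistence among users. Any effect would be indirect, through a different mix of initiators or better counselling.
- **No planned site test.** A reader might infer that a null site difference would be misread as failure of the package. The SAP plans no site test, so that scenario is hypothetical.
- **Raw site contrast.** A simple Nakiwogo-minus-Kigungu difference would not isolate the three components either. There is one community per condition, and the venues differ: temporary public space at Nakiwogo, a health centre at Kigungu.

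A reader might also infer that messaging was certainly new at both sites, or that staff worked across them. The first is undated. On the second, the stakeholder recruitment text in section 6.11a says only "sample can overlap if they deliver care in both communities", a conditional note on interview sampling that does not establish shared providers.

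None of this removes the mismatch within section 5.10a. Leaving Kigungu out of the SAP does not help either, because the before/during estimate then has nothing to set against shared messaging or secular change.

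**Conclusion.** The point holds in two parts of different strength.

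The labelling part is established by the text: study-developed messaging is planned at both sites, Kigungu is nonetheless called standard of care, and the statements must be reconciled.

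The attribution part is conditional. If messaging began with the intervention, the SAP's time coefficient mixes three sources and cannot be assigned to the workshops, calls and supporters. If messaging was in use throughout the pre-period, it adds nothing to the change, although secular change remains and Kigungu's label is still wrong.

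The documents do not support a stated percentage of over- or understatement, nor a claim that the between-site contrast is biased for the three components. The practical consequence is a limit on what the study can conclude, correctable mainly by wording and one added descriptive contrast.

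**What to change.** 1. **Section 5.10a.** Describe Kigungu as standard of care plus Aim 1 messaging. State when messaging began at each site, and when and where the tailored provider training began.
2. **SAP.** Report Kigungu's before/during change in persistence over the same calendar period as Nakiwogo's, beside it, with the difference in changes. Section 5.14b already plans refill dates and durations for both communities. That de-identified file holds no age or gender, so this analysis is unadjusted.
3. **Interpretation, stated in advance.**
   - The Nakiwogo change reflects the three components, any newly started messaging and secular change.
   - The Kigungu change reflects any newly started messaging and secular change.
   - The difference in changes estimates the three components over messaging-enhanced care only if messaging effects and trends are equal at the two sites. Name one community per condition and the different venues as limitations.
4. **Claims.** Do not describe the site comparison as being against standard of care.

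The cost is wording changes, a small amount of descriptive analysis on data already planned, and a narrower claim.

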## \* 5.10b Does this intervention include randomization? Yes No

## \* 5.10c Who will implement the intervention? Check all that apply.

C. External vendor or collaborator

## \* 5.10d List the name(s) of organization(s)

Mildmay Uganda

\* 5.10e Where will the intervention take place (e.g., schools, clinics, participants' homes, military bases, etc.)?

At Nakiwogo, events will be held in a public temporary space (e.g., tent, church) in partnership with Entebbe Hospital, and at Kigungu, Mildmay staff will use space in the nearby public Kigungu Health Center III to test and treat clients during community mobilization events.

# \* 5.10f What will research participants be asked to do as part of the intervention and how much time will it take on average?

Attend at least one 1-hour PrEP workshop, receive ~1 minute check-in calls, select an adherence supporter

# \* 5.10g How often will you administer the intervention to the same research participants during the study?

Participants can attend as many workshops as they would like

#### \* 5.10h What is the expected length of the intervention (in minutes)?

2024-N0127

View: RAND SF: Part 6

## Part 6: Study-level details

#### Introduction

In this section, please provide additional details about your data collection procedures. Major topics covered are: Benefits, risks, incentives, and costs to study participants; recruitment and consent procedures; study inclusion/exclusion criteria; waivers requested; types of sensitive data acquired or accessed; and other pertinent study level details.

When answering these questions, please include details pertaining to all populations and procedures that you previously listed in the matrix.

#### I. Population-specific details

The table below lists the populations identified on your study. Click the Update button next to a population to answer the questions for that population. The Status column indicates whether all questions for the given population have been completed. **Note:** these questions are specific to the population. If you have two similar populations (e.g., two populations of students), make sure both populations appear below. If they don't, go back to Part 4 and add the additional populations as necessary.

1.

Population	Completion Status
Stakeholders (healthcare providers, community leaders, Ministry of Health policymakers)	Completed
Adherence supporters of HIV-negative fisherfolk	Completed
HIV-negative fisherfolk	Completed

#### II. Study-specific details

- 1. Plans to Share Data
- 2. \* 6.13 Do you have any plans to share the individual-level data from your study in identifiable or de-identifiable form?

Yes No

- 3. \* 6.14 Do you have any reason to expect data might be subpoenaed, requested for an administrative procedure or requested by the client?

  Yes No
- 4. Data Safeguarding Plan (DSP)
- 5. \* 6.15 Do you have the Data Safeguarding Plan (DSP) for this study ready to upload in draft or final form? Please use the HSPC template here. Note: If you do not have a DSP

your HSPC approval of your project may be delayed until a DSP is submitted.  $\ensuremath{\mathrm{Yes}}$ 

You can upload the DSP in Part 7 (Project Documents)

